Objectives	
Primary:
 
 To test the non-inferiority of PDT to standard of care surgery by comparing the rate of tumor response after PDT to those observed after surgery, at 24 months post treatment. 
Secondary:
 
 To determine quality of life (QoL) at 6, 12, 18, and 24 months post PDT or surgery. To assess the toxicity using the CTEP NCI Common Terminology Criteria for Adverse Events (CTCAE Version 4.0). 
Tertiary:
 
 Immune markers (T cells). To investigate the correlation of diffuse reflectance optical spectroscopy with tumor response to PDT (Appendix B).
Study Design	
 This is an open-label, randomized, multicenter Phase II study of HPPH-mediated PDT in patients with lesions that are diagnosed as previously untreated T1 N0 or T2 N0 SCC of the oral cavity. 114 participants will be randomized (1:1) to surgery (57) or PDT with HPPH (57). The randomization will be done at RPCI by the biostatistician. Participants will be treated on an outpatient basis. Rarely, participants may require hospitalization, but this will be decided on a case by case basis. All participants will meet the inclusion and exclusion criteria. Participants randomized to PDT with HPPH will be administered a single dose of HPPH at 4 mg/m² via slow intravenous (IV) infusion over 1 hour. Approximately 1 day later, the target tumor will be illuminated with a 665-nm laser light at dose of 140 Joules/cm² delivered at a fluence rate of 150 mW/cm². The participants will be scheduled to have clinical examination at 1 week, 4 - 6 weeks, 12-16 weeks, and at 24 months post therapy. Pathological evaluation will be conducted by taking a 3-mm punch biopsy from the treated region during the 12-16 weeks clinical visit. In the event that a suspicious lesion is observed, the participants will be scheduled for a biopsy at the discretion of the treating physician. Participants will receive standard curative therapy 6 weeks after failing to respond to PDT with HPPH. Tumor response will be determined according to the revised response evaluation criteria in solid tumors (RECIST v1.1).

Target Accrual and Study Duration
	
A maximum of 114 participants at 3 sites, including RPCI, will be enrolled. Accrual is expected to take up to 4 years. Each participant is expected to be on the study for two years and will be followed according to NCCN guidelines.


Study Procedures
	
Disease Evaluation: Baseline and as per the NCCN guidelines for T1/T2 SCC of the head and neck. Quality of Life Questionnaire: Baseline, post treatment at 12 - 16 weeks and 6, 12, 18, and 24 months. Hematology: Baseline. Chemistry: Baseline. Performance Status: Baseline, post treatment at 12 - 16 weeks, and at follow-up visits. Clinical Examination: Baseline and post treatment at 1 week, 4 - 6 weeks, 12 - 16 weeks. We will follow the subjects according to the NCCN guidelines for patients with T1/T2 SCC, i.e. every 3 – 4 months (year 1), 3 – 6 months (year 2). Vital Signs: Baseline, Day 0, post treatment at 1 week, 4 - 6 weeks, 12 - 16 weeks, and at follow-up visits. HPPH Infusion: Day 0 Blood Samples: Day 0, 7, and 4-6 weeks Optical Spectroscopy: Day 1 Laser: Day 1 Adverse Events: From administration of study drug or surgery until 30 days after receiving study drug or surgery.


Statistical Analysis
	
The primary objective of this study is to test the non-inferiority of PDT to standard of care by comparing the rate of tumor response after PDT to those obtained after surgery.
 
This is a randomized multicenter Phase II trial with PDT with HPPH for the treatment of T1/T2 N0 primary tumors of the oral cavity. The design is based on a test for non-inferiority of PDT compared to standard of care with regards to tumor response. Justification for use of a non-inferiority trial is that PDT may be viewed as a potential replacement for standard of care if it is established as less toxic than the standard of care yet still providing acceptable efficacy.
 
Sample Size Determination: The samples sizes of the trial are set at 57 in each of the standard of care and PDT groups. With the proposed sample sizes, there is approximately 80% power associated with the non-inferiority test when the true tumor response probabilities are equal to 85% in both groups.
 
Randomization: The randomization scheme will be generated at RPCI by the biostatistician. 114 participants will be randomized at a ratio of 1:1 to be treated with either standard of care surgery (57) or PDT with HPPH (57).
 
Efficacy Analysis: Objective tumor response will be tabulated overall. All participants who randomized to PDT treatment or surgery will be evaluable for response. Tumor response will be determined by comparing the photographs of the treated site (with reference ruler) before and after PDT or surgery.
 
Safety Analysis: The frequency of toxicities will be tabulated by grade across all cycles. All participants who randomized to HPPH PDT will be considered evaluable for toxicity.

Roswell Park Protocol No.: I 33616

Participant Name (Network sites use participant initials): _____

Medical Record No. (Network sites use participant ID): _____

Title: A Randomized Multicenter Phase II Study Using 2-1[Hexyloxyethyl]-2-Devinylypyropheophorbide-A (HPPH) with PDT versus Standard of Care Surgery for Patients with T1/T2 N0 Squamous Cell Carcinoma of the Oral Cavity

INCLUSION CRITERIA				
Yes	No	N/A	All answers must be "YES or "N/A" for participant enrollment.	Date
			1. Age \geq 18 years of age.	
			2. Have an ECOG Performance Status of \leq 2. Refer to Appendix D .	
			3. Participants with previously untreated T1/T2 N0 squamous cell carcinoma of the oral cavity with or without extension to the oropharynx.	
			4. Histologically confirmed squamous cell carcinoma of the target tumor(s).	
			5. Tumor thickness is 4 mm or less (measured clinically and/or by CT or MRI scan).	
			6. CT or MRI of the neck to confirm staging.	
			7. Tumor accessible for unrestricted illumination for photodynamic therapy (PDT) (accessibility as determined by the physician).	
			8. Life expectancy of at least 12 months in the judgment of the physician.	
			9. Participants of child-bearing potential must agree to use adequate contraceptive methods (e.g., hormonal or barrier method of birth control; abstinence) prior to study entry and for the duration of study participation. Should a woman become pregnant or suspect she is pregnant while she is participating in this study, she should inform her treating physician immediately.	
			10. Participant or legal representative must understand the investigational nature of this study and sign an Institutional Review Board approved written informed consent form prior to receiving any study related procedure.	

Study participant meets all entry criteria: **Yes** **No**

Investigator Signature: _____ **Date:** _____

Roswell Park Protocol No.: I 33616

Participant Name (Network sites use participant initials): _____

Medical Record No.: (Network sites use participant ID): _____

Title: A Randomized Multicenter Phase II Study Using 2-1[Hexyloxyethyl]-2-Devinylypyropheophorbide-A (HPPH) with PDT versus Standard of Care Surgery for Patients with T1/T2 N0 Squamous Cell Carcinoma of the Oral Cavity

EXCLUSION CRITERIA				
Yes	No	N/A	All answers must be "NO" or "N/A" for participant enrollment	Date
			1. Those who have had chemotherapy or radiotherapy or targeted agents within 4 weeks (6 weeks for nitrosoureas or mitomycin C) prior to entering the study or those who have not recovered from adverse events due to agents administered more than 4 weeks earlier.	
			2. Those with known brain metastases should be excluded from this clinical trial because of their poor prognosis and because they often develop progressive neurologic dysfunction that would confound the evaluation of neurologic and other adverse events.	
			3. Those with porphyria or with known hypersensitivity to porphyrins or porphyrin-like compounds.	
			4. WBC < 4,000.	
			5. Those with impaired renal and/or hepatic function, total serum bilirubin > 2 mg/dL, serum creatinine > 2 mg/dL, alkaline phosphatase (hepatic) or SGOT > 3 times the upper normal limit.	
			6. Diagnostic biopsy reveals perineural invasion (PNI) and/or lymphovascular invasion (LVI).	
			7. Uncontrolled intercurrent illness including, but not limited to, ongoing or active infection, symptomatic congestive heart failure, unstable angina pectoris, cardiac arrhythmia, or psychiatric illness/social situations that would limit compliance with study requirements.	
			8. Nodal disease as detected by clinical exam or CT.	
			9. Pregnant or nursing females.	
			10. Unwilling or unable to follow protocol requirements.	
			11. Any condition which in the Investigator's opinion deems the participant an unsuitable candidate to receive study drug.	
			12. Received an investigational agent within 30 days prior to enrollment.	

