4.1.2 Post Treatment Evaluation

Participants will be scheduled to have a clinical examination at 1 week and within 4 - 6 weeks and at 12 – 16 weeks post therapy. In the event that a suspicious lesion is observed, participants will be scheduled for a biopsy at the discretion of the treating physician, at 4-6 weeks post treatment. In addition, a scheduled pathological evaluation will be conducted by taking a 3-mm punch biopsy from the treated tumor site during the clinical visit at 12-16 weeks post therapy.

Tumor response will be determined at 24 months post treatment. The treating physician will examine the clinical response and a photograph of the treatment site will be taken with paper ruler, to determine the reduction in the lesion size, according to RECIST v1.1. A biopsy may be taken, if clinically indicated. The biopsies will be processed following the standard of care pathology. A clinical pathologist will examine the processed tissue section and determine the pathological response.

Participants who have partial or no-response will be offered standard therapy, at the discretion of the treating physician.

We hypothesize that non-responders or partial responders in the PDT arm are likely to be participants whose tumor does not retain HPPH. For this subset of participants that are treated with PDT at RPCI, an additional biopsy (50 mg tissue mass) will be taken at the time of excision of the recurrent tumor to evaluate cellular mechanisms that contribute to tumor retention of HPPH. The biopsy sample is immediately dropped into a sterile 15-ml screw-cap tissue culture tube containing 5 ml of serum-free RPMI medium. A set of such tubes are prepared prior to surgery and can be stored at 4°C for up to a month until use. A research nurse (or other personnel in the operating room, OR) will label the sample tube with an identifier code pertaining to the case, but without inclusion of any PHI. The tube containing the biopsy sample will be placed either into a refrigerator or bucket of ice until pick-up by a member of the investigating laboratories (Drs. [name] or [name], as detailed below). The OR personnel will inform the research associate in the laboratories of either [name] or [name] via telephone or text message. The

associate will pick-up the sample tube at the entrance to the OR and immediately carry it to the laboratory of [name], or [name].

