4.3 MANAGEMENT OF THE NECK AND SALVAGE SURGERY

The management of the neck will be according to standard of care, at the discretion of the treating surgeon. If the participant, based on the pathology of the neck dissection or primary oral cancer resection, has perineural invasion, extracapsular spread, or requires additional therapies including radiation or chemotherapy, they will be dropped from the study and replaced with another participant.

Participants will receive standard curative therapy 6 weeks after failing to respond to PDT with HPPH. All the participants who will have disease progression, local recurrence, or partial or no response (PR, NR) following the PDT with HPPH will be considered treatment failures. The determination will be performed during the study visits, and based on clinical exam and pathology, if clinical exam is unclear.

The surgeon will provide a surgical plan for every patient, including those randomized to PDT. If the patient requires salvage surgery post-PDT, the surgeon will compare the salvage surgery specimen diameter to the diameter of the spot size used for PDT. This data will be used to demonstrate whether PDT affects the surgical plan.

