9.2 TARGET LESIONS

All identifiable lesions will be recorded with digital photography and clinical examination. The objective tumor response will be determined according to the following criteria per Recist v1.1:

- **Complete Response (CR):** Disappearance of all target lesions. Any lymph nodes must have a reduction in short axis to < 10 mm.

- **Partial Response (PR):** At least a 30% decrease in the sum of diameters of target lesions, taking as reference the baseline sum diameters. A biopsy will be taken from the suspected lesions for histological confirmation of squamous cell carcinoma.
- **Progressive Disease (PD):** At least a 20% increase in the sum of diameters of target lesions, taking as references the smallest sum on study (this includes the baseline sum if that is the smallest on study). In addition to the relative increase of 20%, the sum must also demonstrate an absolute increase of at least 5 mm. The appearance of one or more new lesions is also considered progression.
- **Stable Disease (SD):** Neither sufficient shrinkage to qualify for PR nor sufficient increase to qualify for PD, taking as reference the smallest sum diameters while on study, the response will be listed with stable disease. In this case, a biopsy will be taken from the suspected lesion for histological confirmation.

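### Sections 4.1.2, 4.3, 8.8, 9.2, 12.3 and the schedule footnotes give incompatible rules on whether a suspected failure needs histology for the 24-month primary endpoint, so confirmation can differ by arm

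*Combined protocol and SAP*

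**What the plan says.** The rules that bear on confirming a suspected failure are spread over several sections.

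- **Synopsis, Study Design:** "In the event that a suspicious lesion is observed, the participants will be scheduled for a biopsy at the discretion of the treating physician". No visit is named. Section 4.1.2 repeats the clause but ties it to one early visit: "scheduled for a biopsy at the discretion of the treating physician, at 4-6 weeks post treatment".
- **Section 4.1.2, 24-month assessment:** "A biopsy may be taken, if clinically indicated". Sections 8.8 and 12.3 likewise make follow-up histology depend on clinical indication.
- **Footnote 8 to Table 2 (PDT) and footnote 6 to Table 3 (surgery):** identical wording, which adds a biopsy at 2 years to the clinically indicated ones.
- **Section 9.2, PR:** "A biopsy will be taken from the suspected lesions for histological confirmation of squamous cell carcinoma". **SD:** "In this case, a biopsy will be taken from the suspected lesion for histological confirmation". **PD:** no histology is named, and "The appearance of one or more new lesions is also considered progression".
- **Section 4.3:** after PDT, progression, local recurrence, PR and no response are all failures, determined "based on clinical exam and pathology, if clinical exam is unclear". There is no matching definition of failure after surgery.
- **Sections 8.7 and 9.1:** a punch biopsy at 12-16 weeks in both arms.

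Section 12.3 refers the analyst to 9.2 and 9.3 for scoring. The trial is open-label (4.1), and the treating physician assesses the response (4.1.2, 9.1, 12.3).

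**The concern.** A suspicious area at a treated site may be tumour, or it may be scar, ulcer or inflammation. Whether it is biopsied decides whether a false alarm can be recognised. Here that decision depends on which section is followed and on a physician who knows the arm.

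The response categories may also fall differently in the two arms. After excision there is normally no target lesion left to be PR or SD, so a suspected surgical recurrence would tend to be scored as PD or a new lesion, where 9.2 names no histology. Residual PR or SD is mainly a state seen after PDT, where 9.2 does call for it. This is an inference from applying 9.2 to an excised lesion. It is not a written rule.

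The non-inferiority test compares two response proportions with 57 participants per arm, so a few false failures confined to one arm are enough to change its error rate.

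**Working it through.** **1. The sections side by side, for a lesion suspected at the 24-month assessment**

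| Section | Histology for PR or SD | Histology for PD or new lesion |
|---|---|---|
| 9.2 | Yes | Not named |
| 4.1.2, 8.8, 12.3 | If clinically indicated | If clinically indicated |
| Footnotes to Tables 2 and 3 | If clinically indicated, and at 2 years | Same |
| 4.3 (PDT only) | If the examination is unclear | If the examination is unclear |

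These cannot all be followed. A clear PR after PDT must be biopsied under 9.2 and need not be under 4.3. A 2-year visit with nothing suspicious calls for a biopsy under the footnotes and none under 8.8. No section says what a negative biopsy does to a PR or SD call.

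**2. The plan's own figure (12.2)**

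Inputs: 57 per arm, margin 0.20, 85% response in both arms, Farrington-Manning test, power about 80%. The significance level is given as a nominal 0.05 without its sidedness; the two-sided statement comes at the end of the quality-of-life paragraph.

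Power = Φ[(0.20 − z·s0)/s1]. The restricted null rates are 0.708 and 0.908.

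- s0 = √[(0.708×0.292 + 0.908×0.092)/57] = 0.0714
- s1 = √[2×0.85×0.15/57] = 0.0669
- One-sided 0.025 (z = 1.960): (0.20 − 0.1400)/0.0669 = 0.898, power 81.5%
- One-sided 0.05 (z = 1.645): (0.20 − 0.1175)/0.0669 = 1.234, power 89.1%

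The stated 80% fits one-sided 0.025, so that level is used first below.

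**3. Effect of false failures**

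The rejection region of the Farrington-Manning test was enumerated over all 58 × 58 outcomes. The true rates are at the margin: 65% PDT, 85% surgery. A false failure is a true responder scored as a failure; an average of k of them lowers an arm's observed rate by k/57 (1.75 points each). For k = 1, 2, 3 surgery falls to 83.2%, 81.5%, 79.7%, and PDT to 63.2%, 61.5%, 59.7%. The documents give no such counts; k is an assumption.

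Probability of declaring non-inferiority, one-sided 0.025:

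| k | Surgery only | PDT only | Both arms |
|---|---|---|---|
| 0 | 2.6% | 2.6% | 2.6% |
| 1 | 4.2% | 1.5% | 2.6% |
| 2 | 6.5% | 0.9% | 2.6% |
| 3 | 9.6% | 0.5% | 2.6% |

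At one-sided 0.05 the baseline is 5.2%. Surgery only gives 7.9%, 11.5% and 16.1%; PDT only gives 3.2%, 1.9% and 1.1%; equal counts give 5.1-5.2%.

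False failures in PDT only also cost power: at a true 85% in both arms and one-sided 0.025, exact power falls from 83.2% to 74.3%, 64.1% and 53.2% for k = 1, 2, 3.

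**The case against.** A reader might infer more: that PDT failures need histological proof while surgical recurrences count on sight, so the plan is tilted towards non-inferiority. The documents do not support that reading.

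- Section 4.3 lets a clear PR or non-response after PDT be called a failure on examination alone.
- The PD and new-lesion wording in 9.2 applies to both arms, so a PDT recurrence after CR can also go unconfirmed. This could be common. Section 1.3 cites a multicentre PDT trial with 85% CR, maintained in 85% at one year. If the second figure is a share of the complete responders, 0.85 × 0.15 = 12.75% recur after CR against 15% who never reach it, so 12.75/27.75, or 46%, of failures would take the PD route.
- Biopsies are listed for both arms at 12-16 weeks and, in the footnotes, at 2 years.
- Because the effect of a negative biopsy is unstated, nothing shows that histology would clear a PDT lesion.
- The discretion clause in the synopsis is tied by 4.1.2 to 4-6 weeks, whereas 9.3 sets response at 12-16 weeks and 24 months. That clause is not the main conflict.

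All of this stands, and it removes the claim of a fixed direction. It does not remove the conflict between sections. Nor do the scheduled biopsies resolve it: the 12-16 week punch cannot confirm a lesion first seen later, and the 2-year biopsy is not in 4.1.2, 8.8 or 12.3.

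**Conclusion.** The concern holds in this form: the plan contains incompatible rules on histological confirmation for its primary endpoint, and in an open-label trial read by the treating physician this allows confirmation to differ by arm. The direction of any bias is not fixed.

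The size depends on counts that the documents do not give. If all of 1 to 3 false failures fell in surgery, false non-inferiority at one-sided 0.025 would be 4.2% to 9.6% instead of 2.6%. If they all fell in PDT it would be 1.5% to 0.5%, with a loss of power. If they were equal in both arms it would stay at about 2.6%. The test's error rate is therefore sensitive to the difference between arms, which is what a common rule limits. The rule should be set before outcomes are known, because it could not credibly be chosen afterwards by unblinded sites.

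**What to change.** Reconcile 4.1.2, 4.3, 8.8, the footnotes to Tables 2 and 3, 9.2 and 12.3, and bring the synopsis sentence into line with them. Which biopsy schedule is right is for the sponsor and investigators; this review takes no position on it.

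For scoring the endpoint, state one rule in 9.2 and 12.3 for both arms and every category (PR, SD, PD, new lesion at the treated site):

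1. Where a biopsy or salvage specimen exists, score the suspected failure on its histology.
2. State in advance how a negative specimen counts.
3. Where no specimen exists, keep the clinical reading as a failure and flag it as unconfirmed.

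Report confirmed and unconfirmed failures by arm, so that any imbalance is visible. Repeat the primary test counting only confirmed failures. This should be a sensitivity analysis and not a replacement, because it would also drop clinically clear PDT failures that have no specimen, which favours PDT.

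The cost is protocol wording, one CRF field and one extra analysis. The scoring rule adds no procedure. The limitation is that some failures remain clinically defined, so the rule reduces arm-dependent confirmation and exposes what is left without removing it entirely.

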8.6 ABOUT 4 - 6 WEEKS POST TREATMENT

- Clinical examination with photograph of lesion if possible
- Vital signs (i.e., temperature, heart rate, respiratory rate, blood pressure, and body weight)
- Correlative studies blood samples (for participants randomized to PDT only)
- Normal tissue toxicity grade (for participants randomized to PDT only) (**Appendix F**)
- Adverse events

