12.2 SAMPLE SIZE DETERMINATION

In the proposed randomized trial, participants will be randomized to the treatment arms using a stratified block randomization scheme, with blocking stratified by clinical site (RPCI, and two other participating sites). Participants will be included in data analyses according to their randomized treatment assignment irrespective of the treatment actually received (intent-to-treat). Exceptions would include those who withdraw their consent to use any of their data prior to receiving any study medication. Initiation of study treatment will take place as soon as possible following randomization. No method of imputation will be used for missing data. All available data from participants who fail to complete this study will be included in all safety summaries.

The safety of the interventions will be assessed through the evaluation of Grade 3 or higher toxicities deemed possibly related to treatment. Both efficacy (e.g., tumor response) and toxicity rates will be estimated using simple relative frequencies. The corresponding 95% confidence intervals for the estimated probabilities will be computed using the method proposed in Clopper and Pearson (1934).

The design for this study is based on a test for non-inferiority of PDT compared to standard of care with regards to tumor response at 24 months post-procedure. Justification for use of a non-inferiority trial is that PDT may be viewed as a potential replacement for standard of care if it is established as less toxic than the standard of care yet still providing acceptable efficacy. Let π_{SOC}

and π_{PDT} are the probabilities of tumor response in the standard of care and PDT groups, respectively. The hypotheses corresponding to the proposed non-inferiority trial are

$$H_0 : \pi_{PDT} \leq \pi_{SOC} - \Delta,$$
$$H_a : \pi_{PDT} > \pi_{SOC} - \Delta,$$

where Δ is the non-inferiority margin. Specifically, we will be using the approach of Farrington-Manning to test our hypothesis via a score based test.⁵³

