12.4 ADVERSE EVENT

The frequency of toxicities will be tabulated by grade. All participants who receive any study treatment will be considered evaluable for toxicity.

RPCI may terminate the study at any time upon immediate notice if it believes termination is necessary for the safety of participants enrolled in the study.

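### The synopsis limits the toxicity set to the PDT arm, against section 12.4, and no between-arm toxicity estimate is planned although the non-inferiority rationale refers to PDT being less toxic

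*Combined protocol and SAP*

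**What the plan says.** The Safety Analysis paragraph of the synopsis defines the toxicity set by randomization to one arm: "All participants who randomized to HPPH PDT will be considered evaluable for toxicity". The Efficacy Analysis paragraph just before it names both PDT and surgery.

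Section 12.4 defines the set by treatment received and names no arm: "All participants who receive any study treatment will be considered evaluable for toxicity". Its only planned analysis is: "The frequency of toxicities will be tabulated by grade".

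Section 12.2 adds a measure: "The safety of the interventions will be assessed through the evaluation of Grade 3 or higher toxicities deemed possibly related to treatment". It then says: "Both efficacy (e.g., tumor response) and toxicity rates will be estimated using simple relative frequencies", and: "The corresponding 95% confidence intervals for the estimated probabilities will be computed using the method proposed in Clopper and Pearson (1934".

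The same section, like the synopsis, gives the reason for a non-inferiority design: PDT might come to replace standard of care "if it is established as less toxic than the standard of care yet still providing acceptable efficacy".

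Adverse events are collected in both arms. The synopsis runs the window from study drug or surgery to 30 days afterwards, and Table 3 schedules adverse events for surgery participants at about 1 week and 4-6 weeks.

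**The concern.** Two definitions of one analysis set cannot both be applied. They differ in arm coverage (PDT alone against all treated) and in basis (randomized against treated). A statistician working from the synopsis would produce no toxicity table for surgery, and the collected surgery-arm data would go unused.

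Correcting the set does not finish the job. Being less toxic is a statement about a contrast, and the plan has no toxicity contrast: no difference, no interval for a difference, and no instruction to tabulate by arm. The trial could report non-inferior response and leave readers to assemble the toxicity side themselves, with an analysis chosen after the data are known.

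**Working it through.** **Set definitions side by side**

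| Place | Who is evaluable for toxicity | Surgery arm |
|---|---|---|
| Synopsis, Safety Analysis | Randomized to HPPH PDT | Not named |
| Section 12.4 | Received any study treatment | Included, if surgery counts as study treatment |

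The wider reading of 12.4 is well supported. Section 8.4 lists surgery and laser PDT together as the Day 1 treatment, 12.2 speaks of interventions in the plural, and adverse events are collected after surgery. But 12.4 does not say outright that surgery is study treatment. On the synopsis rule, 114 - 57 = 57 participants fall outside the set.

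**Planned toxicity analyses.** Sections 12.2 and 12.4 give tabulation by grade, simple rates and Clopper-Pearson intervals. Between-group contrasts appear only in the quality-of-life paragraph of 12.2. The toxicity objective in 3.2 is to assess, not to compare.

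**Whether surgery-arm events can be counted alike.** Section 12.2 counts toxicities possibly related to treatment, but the relationship categories in 10.1.2 are defined against the study drug. Surgery participants receive no study drug, so the categories do not say how a surgical complication should be rated. The serious-event window in 10.2.2 runs from HPPH infusion or PDT light, with no equivalent for surgery.

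**Precision of a difference.** The plan has no precision or power figure for toxicity to reproduce; its approximately 80% power concerns tumor response. The one design input is n = 57 per arm (12.2). The documents give no surgical toxicity rate, so the rates p below are assumptions, taken as equal in both arms.

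Half-width of the 95% interval (simple normal approximation) = 1.96 × √(2p(1 - p)/57)

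- p = 10%: 1.96 × √(2 × 0.10 × 0.90/57) = 0.110
- p = 20%: 1.96 × √(2 × 0.20 × 0.80/57) = 0.147
- p = 30%: 1.96 × √(2 × 0.30 × 0.70/57) = 0.168
- p = 40%: 1.96 × √(2 × 0.40 × 0.60/57) = 0.180

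**What arm-level intervals leave open.** Suppose 6 of 57 PDT and 11 of 57 surgery participants have an event (invented counts). The Clopper-Pearson intervals are 4.0% to 21.5% and 10.0% to 31.9%. They overlap, and neither gives the contrast. The difference is (6 - 11)/57 = -8.8 points. Its half-width is 1.96 × √[(6 × 51 + 11 × 46)/57³] = 0.130, so the interval runs from about -22 to +4 points.

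**Power, for orientation.** With a two-sided 0.05 test and 57 per arm, power is 23% for 30% against 20%, 48% for 30% against 15%, and 65% for 40% against 20%.

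**The case against.** The strongest defence is that the synopsis is a summary. It does not say that only PDT participants count, and 12.4 with 12.2 already gives grade 3 or higher rates with 95% intervals for the interventions. The toxicity objective is to assess. The replacement sentence looks ahead to eventual use, and 12.1 expects a confirmatory phase III trial. The lasting morbidity that PDT is meant to avoid (speech, swallowing) is compared between arms through the quality-of-life contrasts to 24 months, whereas adverse events are collected for 30 days. An added toxicity contrast would have low power.

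Much of this stands. Safety is not left unanalysed, longer-term morbidity belongs to the quality-of-life analysis, and the added contrast can only be descriptive. What remains is that two definitions conflict, the contrast named in the rationale is not estimated, and events after surgery lack a common counting basis.

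A reader might infer three stronger points that the documents do not support:

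- **That lower toxicity is what justifies the 20-point margin.** Section 12.1 rests the margin on an analogy with FDA bioequivalence rules and on the phase II purpose, and adds that PDT failures can be salvaged surgically. The toxicity sentence supports the choice of a non-inferiority design, not the size of the margin.
- **That the design is justified only if this trial shows PDT to be less toxic.** Section 12.2 makes lower toxicity a condition on possible replacement. It does not require this trial to prove it.
- **That 8.6 contradicts Table 3.** Section 8.6 has "Normal tissue toxicity grade (for participants randomized to PDT only", with reference to Appendix F, whose note concerns tissue in the light field. Table 3 has a differently named toxicity-grade row that does not cite Appendix F. These may be two different scales, so no contradiction is shown.

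**Conclusion.** The concern holds in two parts. First, the synopsis and 12.4 define different toxicity sets, and the synopsis version, followed literally, omits 57 of 114 participants whose adverse events are collected. That count rests on reading the synopsis as exclusive, which its contrast with the neighbouring efficacy paragraph supports. Second, no between-arm toxicity estimate is planned, although the rationale for the design speaks of PDT being less toxic.

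At 57 per arm a difference would carry a 95% half-width of about 11 points at an assumed 10% rate in each arm, 15 at 20%, and 17 to 18 at 30% to 40%. This is enough to describe the contrast, but not to establish a moderate advantage. The point should be corrected before analysis. It does not touch the primary non-inferiority test.

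**What to change.** 1. Replace the synopsis sentence with the 12.4 set. State in both places that it covers both arms, that surgery counts as study treatment, and that toxicity is tabulated by arm.
2. Add to 12.4 the PDT-minus-surgery difference in the proportion of participants with at least one grade 3 or higher toxicity judged possibly related to treatment, with a 95% score interval, labelled descriptive. Keeping the relatedness condition of 12.2 avoids creating a second, inconsistent measure.
3. Reconcile the attribution wording in 10.1.2 and the serious-event window in 10.2.2 so that events after surgery are counted on the same basis as events after PDT.
4. Note beside the result that adverse events cover 30 days and that longer-term morbidity is addressed by the quality-of-life contrasts.

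The cost is small: no added participants or visits. Items 1, 2 and 4 are wording. Item 3 goes a little further, because it changes how sites attribute and report surgery-arm events. It should be settled while those events can still be classified in a uniform way.
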